2. SUMMARY OF KEY PROTOCOL INFORMATION

2.1. Changes to the Protocol Defined Statistical Analysis Plan

There were no changes or deviations to the originally planned statistical analysis specified in the protocol (Dated: 23/JUL/2018).

C_{8h} has been collected as a PK endpoint since dosing in the PoC studies (203167 (psoriasis), 203168 (rheumatoid arthritis) and 202152 (ulcerative colitis)) was changed from BID to TID dosing with the immediate release (IR) formulation of GSK2982772. On further reflection, comparisons of C_{8h} and C_{12h} following single dose are not relevant comparisons and will not be included in the analyses.

2.2. Study Objective(s) and Endpoint(s)

Objectives	Endpoints	
Primary Objectives	Primary Endpoints	
To evaluate the single dose PK profile of GSK2982772 from each MR prototype coated tablet formulation (240 mg) compared to the IR formulation (240 mg) (Part A)	GSK2982772 area under the curve from time zero to infinity (AUC(0-inf)), area under the curve from time zero to the last measurable concentration (AUC(0-t)), area under the curve from time zero to 24 hours (AUC(0-24)), maximum observed concentration (Cmax), concentration at 24 hours post-dose (C24h), time to Cmax (Tmax), terminal half-life (t1/2).	
To assess the impact of a high-fat breakfast on the PK of GSK2982772 following single dose administration of one or more selected MR prototype coated tablet formulations (240 mg) (Part A or Optional Part B) Secondary Objectives	GSK2982772 AUC(0-inf), AUC(0-t), Cmax, Tmax, C24h, and t1/2, relative bioavailability (FrelFE), relative bioavailability (FrelFormulation) to IR based on AUC and Cmax Secondary Endpoints	
	 	
 To assess the safety and tolerability 	Adverse events (AEs)	

Ob	jectives	End	dpoints
	of single doses of GSK2982772 (Part A)	•	Clinical laboratory values (clinical chemistry, haematology and urinalysis) Vital sign measurements (blood pressure, heart rate, respiratory rate and body temperature) 12-Lead electrocardiogram (ECG) monitoring
•	To determine the bioavailability of GSK2982772 MR prototype coated tablet formulations relative to the IR reference, as appropriate (Part A) [1]	•	Relative bioavailability (Frelformulation) based on AUC and Cmax
	oloratory Objectives	_	oloratory Endpoints
•	To assess the safety and tolerability of single doses of GSK2982772 (Optional Part B)	• • • mo	Adverse events (AEs) Clinical laboratory values (clinical chemistry, haematology and urinalysis) Vital sign measurements (blood pressure, heart rate, respiratory rate and body temperature) 12-Lead electrocardiogram (ECG) nitoring
•	To evaluate the PK profile of alternative tablet strengths of selected GSK2982772 MR prototype coated tablet formulations (Optional Part B)	•	GSK2982772 AUC(0-inf), AUC(0-t), AUC(0-24), Cmax, C24h, t1/2, AUC/Dose and Cmax/Dose
•	To evaluate the impact of dosing 2 or more MR prototype coated tablets on the PK profile of GSK2982772 (Optional Part B)	•	GSK2982772 AUC(0-inf), AUC(0-t) or AUC(0-24), Cmax, Tmax and t1/2
•	To determine if there are any dose dependent changes in the absorption of GSK2982772 following single dose administration selected GSK2982772 MR prototype coated tablet formulations (Optional Part B)	•	GSK2982772 AUC(0-inf), AUC(0-t), AUC(0-24), Cmax, C24h and Tmax
•	To assess the impact of a standard breakfast on the PK of GSK2982772 following single dose administration of one or more selected MR prototype coated tablet formulations (240 mg) (Part A - optional)	•	GSK2982772 AUC(0-inf), AUC(0-t), Cmax, Tmax and t1/2, relative bioavailability (FrelFe), relative bioavailability (FrelFormulation), based on AUC and Cmax
•	To assess the impact of a delayed meal on the PK of GSK2982772 following single dose administration of one or more selected MR prototype coated tablet formulations (240 mg) (Part A - optional)	•	GSK2982772 AUC(0-inf), AUC(0-t), Cmax, Tmax and t1/2, relative bioavailability (FrelFe), relative bioavailability (FrelFormulation), based on AUC and Cmax

2.3. Study Design

See Section 5 of the protocol for the study design.

2.4. Statistical Hypotheses / Statistical Analyses

No formal hypothesis will be tested. However, point estimates and corresponding 90% confidence intervals will be derived for Cmax, AUC(0-t), AUC(0-inf) and C24h.

3. PLANNED ANALYSES

3.1. Interim Analyses

No formal statistical analyses are planned. However, after Period 3 of Part A is complete, the PK data will be analysed which will guide Periods 4, 5 and 6. Periods 4, 5 and 6 will be flexible and the dosing regimen will be dependent on the outcome (safety and PK) of preceding periods. There will be the option to optimise the MR release duration and/or to evaluate the impact of a high-fat, standard, or delayed meal on the selected MR formulation(s). If an optimal formulation is identified in Part A, Part B will proceed. If none of the MR prototype coated tablet formulations are suitable, then Part B of the study may not be conducted or Part B may be used to continue to optimise the MR prototype coated tablet formulations. This will be based upon identifying a formulation that has an appropriate exposure profile that does not show a significant food effect.

In Part B, there will be an interim review following completion of each of Periods 1 to 5 to determine the dose level, formulation and prandial status, as appropriate, to be used in subsequent periods.

3.2. Final Analyses

The final planned primary analyses will be performed after the completion of the following sequential steps:

- 1. All participants have completed the study as defined in the protocol
- 2. All required database cleaning activities have been completed and final database release (DBR) and database freeze (DBF) has been declared by Data Management.

4. ANALYSIS POPULATIONS

Population	Definition / Criteria	Analyses Evaluated
All Subjects	 All participants who were screened for eligibility and allocated a subject number. 	Selected Study Population
Safety	All participants who receive at least 1 dose of study	 Safety and Study

Population	Definition / Criteria	Analyses Evaluated
	treatment and will be the population for reporting of safety and study population data. Participants will be analyzed according to the treatment they actually received.	Population
PK	Participants in the 'Safety Population' for whom a PK sample was obtained and analysed will be the population for reporting of PK data.	• PK

Refer to Appendix 10: List of Data Displays which details the population used for each display.

4.1. Protocol Deviations

Important protocol deviations (including deviations related to study inclusion/exclusion criteria, conduct of the trial, patient management or patient assessment) will be summarised and listed.

Protocol deviations will be tracked by the study team throughout the conduct of the study in accordance with the Protocol Deviation Management Plan (PDMP) [26-APR-2019 version 1.01]. See Section 10.1 for further details.

A separate summary and listing of all inclusion/exclusion criteria deviations will also be provided. This summary will be based on data as recorded on the inclusion/exclusion page of the eCRF.

5. CONSIDERATIONS FOR DATA ANALYSES AND DATA HANDLING CONVENTIONS

5.1. Study Treatment & Sub-group Display Descriptors

	Treatment Group Descriptions									
	RandAll NG	Data Displays for Re	porting							
Code	Description	Description	Order in TLF							
Part A										
Α	GSK2982772 240mg MR RR1 oral single dose	MR-12h 240mg Fasted	2							
В*	GSK2982772 240mg MR RR2 oral single dose	IR 240mg Fasted	1							
C*	GSK2982772 240mg IR oral single dose	MR-18h 240mg Fasted	3							
D	GSK2982772 240mg MR RR3 oral single dose	MR-18h 240mg Fed (High-Fat)	5							
E	GSK2982772 240mg MR RR4 oral single dose	MR-12h 240mg Fed (High-Fat)	4							
F	GSK2982772 240mg MR fed state	MR-16h 240mg Fasted	6							
Part B		 								
G	GSK2982772 120mg MR oral single dose	MR-16h 480mg Fasted	1							
Н	GSK2982772 480mg MR oral single dose	MR-16h 960mg Fasted	5							
J	GSK2982772 MR oral single dose 1	MR-16h 480mg Fed (High-Fat)	3							
K	GSK2982772 MR oral single dose 2	MR-16h 120mg Fasted	6							
L	GSK2982772 MR oral single dose 3	MR-16h 480mg Fed (High-Fat) (Enteric Coated)	4							
М	GSK2982772 MR oral single dose 4	MR-16h 480mg Fed (Standard)	2							

^{*} In Part A, the treatments for Period 2 and 3 were reversed in order due to availability of the drug at site. For Period 2 participants received "GSK2982772 240mg IR oral single dose" and Period 3 participants received "GSK2982772 240mg MR RR2 oral single dose".

Safety listings may be presented chronologically instead of in the order suggested above.

5.2. Baseline Definitions

For all endpoints (except as noted in baseline definitions) the baseline value will be the latest pre-dose assessment with a non-missing value, including those from unscheduled visits. If time is not collected, Day 1 assessments are assumed to be taken prior to first dose and used as baseline. Unless otherwise stated, the mean of replicate assessments at any given time point will be used as the value for that time point.

Parameter	Study Asses	Baseline Used in Data Display			
	Screening Day -1 Day 1 (Pre-Dose				
Safety					
Vital signs	X	Χ	X	Day 1 (Pre-Dose)	
12-lead ECG	X	Χ	X	Day 1 (Pre-Dose)	
Laboratory (Haematology, clinical chemistry and urinalysis)	Х	Х	Х	Day 1 (Pre-Dose)	

Unless otherwise stated, if baseline data is missing no derivation will be performed and baseline will be set to missing.

5.3. Multicentre Studies

This is a single centre study.

5.4. Examination of Covariates, Other Strata and Subgroups

There are no covariates, strata or subgroups to be investigated in this study.

5.5. Multiple Comparisons and Multiplicity

No adjustments for multiplicity will be required.

5.6. Other Considerations for Data Analyses and Data Handling Conventions

Other considerations for data analyses and data handling conventions are outlined in the appendices:

Section	Component
10.3	Appendix 3: Assessment Windows
10.4	Appendix 4: Study Phases and Treatment Emergent Adverse Events

Section	Component
10.5	Appendix 5: Data Display Standards & Handling Conventions
10.6	Appendix 6: Derived and Transformed Data
10.7	Appendix 7: Reporting Standards for Missing Data
10.8	Appendix 8: Values of Potential Clinical Importance

6. STUDY POPULATION ANALYSES

6.1. Overview of Planned Study Population Analyses

The study population analyses will be based on the Safety population, unless otherwise specified.

Study population analyses including analyses of subject's disposition, protocol deviations, demographic and baseline characteristics, prior and concomitant medications, and exposure will be based on GSK Core Data Standards. Details of the planned displays are presented in Appendix 10: List of Data Displays.

7. SAFETY ANALYSES

The safety analyses will be based on the Safety population, unless otherwise specified.

7.1. Adverse Events Analyses

Adverse events analyses including the analysis of adverse events (AEs), Serious Adverse Events (SAEs) and other significant AEs will be based on GSK Core Data Standards. The details of the planned displays are provided in Appendix 10: List of Data Displays.

7.2. Clinical Laboratory Analyses

Laboratory evaluations including the analyses of Chemistry laboratory tests, Hematology laboratory tests, Urinalysis, and liver function tests will be based on GSK Core Data Standards. The details of the planned displays are provided in Appendix 10: List of Data Displays.

In additional to GSK Core Data Standards, Lipids (Total Cholesterol and Triglycerides) outside the normal range will be summarised.

7.3. Other Safety Analyses

The analyses of non-laboratory safety test results including ECGs and vital signs will be based on GSK Core Data Standards, unless otherwise specified. The details of the planned displays are provided in Appendix 10: List of Data Displays.

8. PHARMACOKINETIC ANALYSES

8.1. Primary, Secondary, and Exploratory Pharmacokinetic Analyses – Part A and Part B

8.1.1. Endpoint / Variables

8.1.1.1. Drug Concentration Measures

Refer to Appendix 5: Data Display Standards & Handling Conventions (Section 10.5.2 Reporting Standards)

8.1.1.2. Derived Pharmacokinetic Parameters

Pharmacokinetic parameters will be calculated by standard non-compartmental analysis according to current working practices and using the currently supported version of WinNonlin. All calculations of non-compartmental parameters will be based on actual sampling times. Pharmacokinetic parameters listed will be determined from the plasma concentration-time data, as data permits.

Parameter	Parameter Description
AUC _(0-inf)	Area under the curve from time zero to infinity
AUC _(0-t)	Area under the curve from time zero to the last quantifiable concentration
AUC ₍₀₋₂₄₎	Area under the curve from time zero to 24 hours
AUC%extrap	Percentage of AUC extrapolated beyond the last measured time point.
t _{1/2}	Terminal half-life
T _{lag}	Time from dosing to first quantifiable concentration.
T _{last}	Time of last measurable concentration
T _{max}	Time of maximum observed concentration
C _{max}	Maximum observed concentration
C _{24h}	Concentration at 24 hours post-dose

NOTES:

- Additional parameters may be included as required.
- No log transformation for Tmax nor any ratio (relative) endpoint.

8.1.2. Summary Measure

For each period in Part A and Part B period, descriptive statistics (n, arithmetic mean, standard deviation [SD], 95% CI, minimum, median and maximum) will be calculated by treatment for all PK concentrations over time and for the derived PK parameters. In addition, for loge-transformed PK parameter variables geometric mean, 95% CI and %CVb (100 * $\sqrt{\exp(\text{SD2})}$ -1)) will be provided, where the SD is the standard deviation of log-transformed data.

8.1.3. Population of Interest

The primary pharmacokinetic analyses will be based on the Pharmacokinetic population, unless otherwise specified.

8.1.4. Strategy for Intercurrent (Post-Randomization) Events

- Subject study completion (i.e. as specified in the protocol) was defined as completing all phases of the study including the follow-up visit.
- Withdrawn subjects may be replaced in the study. Replacement subjects enrolled will be dosed with the next planned treatment of the withdrawn subject, and they will not receive any treatment that the withdrawn subject has already received with the exception of the need to increase subject numbers to obtain the minimum number of evaluable subjects required for interim decisions, and to obtain data in any other treatment that is required for a valid comparison. Replacement subjects will receive the required treatments in the same order as planned for the original subject and the minimum washout period will be respected with regard to the timing of dosing of the IR formulation.
- All available data from subjects who were withdrawn from the study will be listed
 and all available planned data will be included in summary tables and figures, unless
 otherwise specified.

8.1.5. Statistical Analyses / Methods

Details of the planned displays are provided in Appendix 10: List of Data Displays and will be based on GSK Data Standards and statistical principles.

Unless otherwise specified, endpoints / variables defined in Section 8.1.1 will be summarised using descriptive statistics, graphically presented (where appropriate) and listed.

8.1.5.1. Statistical Methodology Specification

The following pharmacokinetic statistical analyses will only be performed if sufficient data is available (i.e. if participants have well defined plasma profiles).

Parts A and B

Model Specification: AUC, C_{max}, C_{24h} in log scale

- Include covariates and handling of multicentre studies (if appropriate), additional information can be included in other relevant sections of the RAP and cross reference provided.
- For each study part and each endpoint a mixed model will be fit with up to 6 observations per participant expected in Part A, corresponding to periods 1 through 6. Similarly for Part B. The model will contain formulation (PATRTGRP) as a fixed, categorical effect, and a random intercept for subject.
- The Kenward and Roger method for approximating the denominator degrees of freedom and correcting for bias in the estimated variance-covariance of the fixed effects will be used.

Model Checking & Diagnostics

- Model assumptions will be applied, but appropriate adjustments may be made based on the data.
- In the event the model fails to converge, the RANDOM statement will be removed and
 alternative covariance structures such as CS, CSH, or UN for the R matrix will be used by
 specifying 'type=' on the REPEATED line. Akaike's Information Criteria (AIC) will be used to
 assist with the selection of covariance structure.
- Distributional assumptions underlying the model used for analysis will be examined by
 obtaining a normal probability plot of the residuals and a plot of the residuals versus the fitted
 values (i.e. checking the normality assumption and constant variance assumption of the model
 respectively) to gain confidence that the model assumptions are reasonable.
- If there are any departures from the distributional assumptions, alternative models will be explored using appropriate transformed data.

Model Results Presentation

- Point estimates and corresponding 90% CI will be computed for the differences in the endpoint for each treatment period.
- The relative bioavailability ratio, Frel, and 90% CI will be calculated by back-transforming the
 difference between the least square means for each of the two formulation comparisons. See
 Section 10.6.4

Model Specification: Tmax

- Include covariates and handling of multicentre studies (if appropriate), additional information can be included in other relevant sections of the RAP and cross reference provided.
- Exact non-parametric Hodges-Lehmann estimation of location shift will be fitted.

Model Results Presentation

 For each relative bioavailability, the median difference and 90% CI for median difference will be presented.

Part A - Formulation

Endpoint (AUC, C_{max}, C_{24h} in log scale)

- AUC_(0-inf)
- AUC_(0-t)
- AUC_(0-24h)
- C_{max}
- C_{24h}
- T_{max}

Relative Bioavailability

- MR-12h 240mg Fasted vs IR 240mg Fasted
- MR-18h 240mg Fasted vs IR 240mg Fasted

- MR-16h 240mg Fasted vs IR 240mg Fasted
- MR-18h 240mg Fed (High-Fat) vs MR-12h 240mg Fed (High-Fat)

Part A – Food Effect

Endpoint (AUC, Cmax in log scale)

- AUC_(0-inf)
- AUC_(0-t)
- C_{max}
- T_{max}

Relative Bioavailability

- MR-18h 240mg Fed (High-Fat) vs MR-18h 240mg Fasted
- MR-12h 240mg Fed (High-Fat) vs MR-12h 240mg Fasted

Part B – Dose Effect

Endpoint (AUC, C_{max}, C_{24h} in log scale)

- AUC_(0-inf)
- AUC_(0-t)
- AUC_(0-24h)
- C_{max}
- C_{24h}
- T_{max}

Relative Bioavailability

- MR-16h 960mg Fasted vs MR-16h 120mg Fasted
- MR-16h 480mg Fasted vs MR-16h 120mg Fasted
- MR-16h 960mg Fasted vs MR-16h 480mg Fasted

Part B – Food Effect

Endpoint (AUC, Cmax in log scale)

- AUC_(0-inf)
- AUC_(0-t)
- C_{max}
- T_{max}

Relative Bioavailability

• MR-16h 480mg Fed (High-Fat) vs MR-16h 480mg Fasted

Part B – Enteric Coating Effect

Endpoint (AUC, C_{max}, C_{24h} in log scale)

- AUC_(0-inf)
- AUC_(0-t)
- C_{max}
- C_{24h}
- T_{max}

Relative Bioavailability

• MR-16h 480mg Fed (High-Fat) (Enteric Coating) vs MR-16h 480mg Fed (High-Fat)

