Primary	The primary endpoints for food effect will be summarised descriptively. In addition, log-transformed AUC _(0-inf) (AUC _(0-t) , if AUC _(0-inf) cannot be derived), C _{24h} , and C _{max} will be analysed using a mixed effects model with regimen as a fixed effect and subject within sequence as a random effect. Point estimates and corresponding 90% CI will

Endpoint	Statistical Analysis Methods
	be computed for the differences in GSK2982772 MR formulation taken in the fed state (test) vs in the fasted state (reference) using the residual error from the model (MSE). The point and interval estimates on the log-scale will then be exponentially back transformed to give estimates of the ratios of geometric means and 90% CI.
	Within-subject coefficients of variation for $AUC_{(0-inf)}$ and C_{max} will be calculated based on the log _e -Normal distribution: CV_w (%) = sqrt[exp(mse) - 1] x 100, where MSE is the residual error from the model.
	Statistical analysis of the PK endpoint T_{max} of GSK2982772 MR formulation administered under both fed and fasted conditions will be separately analysed non- parametrically [Hauschke, 1990]. The point estimates for the medians for each treatment, the median difference and 90% CI for the median difference will be calculated for the contrast (test-reference).
Secondary	The secondary PK endpoints for the selected MR formulations at different tablet strengths and multiple dose units will be summarised descriptively.
	For Part B, plots of dose vs dose normalised AUC ₍₀₋₂₄₎ , C_{24h} and C_{max} will be generated to determine if there are any dose dependent changes in the absorption of GSK2982772 following administration of different tablet strengths and multiple dose units of the selected MR formulation(s).
	For Part B, dose proportionality will be assessed by visual inspection of dose normalised AUC ₍₀₋₂₄₎ , AUC _(0-inf) [or if not available AUC _(0-t)] and C _{max} values versus dose. Analysis of these log _e -transformed parameters may be carried out, using the power model.
	For Part B Period 7, the relative bioavailability of time effect (Frel(time effect)) will be assessed by comparing $AUC_{(0-inf)}$, $AUC_{(0-t)}$, C_{max} , T_{max} , between evening dosing (test) versus morning dosing in the same prandial state (reference).

The Reporting and Analysis Plan will describe the planned PK analyses in greater detail.

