10.6.5. Pharmacokinetic

The pharmacokinetic parameters will be calculated by standard non-compartmental analysis according to current working practices using WinNonlin Version 6.3 or higher.

Pharmacokinetic Endpoints

AUC(0-t)

Area under the concentration-time curve from time zero to the time of the last quantifiable concentration
(C(t)) will be calculated using the linear trapezoidal rule for each incremental trapezoid and the log
trapezoidal rule for each decremental trapezoid.

AUC(0-∞)

• Area under the concentration-time curve extrapolated to infinity will be calculated as:

$$AUC = AUC(0-t) + C(t) / lambda_z$$

where lambda z is the terminal phase rate constant.

Pharmacokinetic Endpoints

AUC(0-24)

Area under the concentration-time curve from time zero to 24 h post dose will be calculated using the linear trapezoidal rule for each incremental trapezoid and the log trapezoidal rule for each decremental trapezoid.

AUC%extrap

Percentage of AUC extrapolated beyond the last measured time point

C_{max}

Maximum observed concentration, determined directly from the concentration-time data

C_{24h}

Observed concentration at 24 hours, determined directly from the concentration-time data

Tmax

Time to reach Cmax, determined directly from the concentration-time data.

Tlast

Time of last measurable concentration

Tlag

Time from dosing at which GSK2982772 was first quantifiable in a concentration vs time profile

t1/2

Terminal half-life

Notes

Additional parameters may be included as required

Relative Bioavailability (Frel)

• Frel will be calculated as follows:

$$Frel = \frac{GeoMean\{AUC\ or\ C_{max}(test)\}}{GeoMean\{AUC\ or\ C_{max}(reference)\}} \times 100$$
Fred will be calculated using AUC on AUC (0 less). Given and

Frel will be calculated using AUC_(0-inf), AUC(0-last), C_{24h}, and C_{max}.

- MR Formulation (test) vs IR Formulation (reference)
- MR Fed (test) vs MR Fasted (reference)
- Enteric Coated (test) vs MR (reference)

MR refers to DiffCORE

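### The SAP's food-effect analyses leave out C24h, which the protocol requires to be modelled fed versus fasted, and no removal is declared

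*SAP*

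**What the plan says.** **Protocol.** The primary food-effect row of the analysis table in 10.4.1 names three log-transformed parameters: AUC(0-inf) (AUC(0-t) as fallback), C24h and Cmax. These "will be analysed using a mixed effects model with regimen as a fixed effect and subject within sequence as a random effect". Point estimates and 90% CIs are to "be computed for the differences in GSK2982772 MR formulation taken in the fed state (test) vs in the fasted state (reference"), then back-transformed to ratios of geometric means. Protocol section 4 lists C24h among the endpoints of the primary high-fat objective, which is worded for 240 mg. Protocol 10.1 promises point estimates and 90% CIs for C24h.

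**SAP, consistent with the protocol.** SAP 2.2 repeats the high-fat endpoint set: "GSK2982772 AUC(0-inf), AUC(0-t), Cmax, Tmax, C24h, and t1/2, relative bioavailability (FrelFE"). SAP 2.4 again promises a 90% CI for C24h, with no exception for food effect. The general model in 8.1.5.1 is headed "Model Specification: AUC, C_{max}, C_{24h} in log scale". Appendix 6 (10.6.5) says "Frel will be calculated using AUC_(0-inf), AUC(0-last), C_{24h}, and C_{max"}, and its comparisons include "MR Fed (test) vs MR Fasted (reference").

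**SAP, not consistent.** The Part A and Part B food-effect blocks of 8.1.5.1 are headed "Endpoint (AUC, Cmax in log scale") and list AUC(0-inf), AUC(0-t), Cmax and Tmax only.

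**Declared changes.** SAP 2.1 states: "There were no changes or deviations to the originally planned statistical analysis specified in the protocol (Dated: 23/JUL/2018"). The only comparisons it drops are those of C8h and C12h.

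**The concern.** The endpoint-and-contrast blocks of 8.1.5.1 are the operative instruction, because they say which parameters are estimated for which pair of regimens. If they are followed, the report will lack a fed/fasted ratio and 90% CI for C24h.

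That estimate matters for this study. Protocol 5.1.3 describes the aim as a once-daily product with as high a minimum concentration as possible, and Part A seeks a formulation without a clinically significant food effect. For once-daily dosing, C24h is the end-of-interval concentration, so its fed/fasted ratio bears on both aims.

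SAP 5.1 already names the specific regimens dosed, and protocol 5.1.3 lists C24h among the parameters supplied for interim decisions. A protocol-specified estimate dropped at that stage should be declared. The pattern looks like an oversight, and nothing in the documents suggests otherwise.

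**Working it through.** **1. Endpoint blocks in SAP 8.1.5.1**

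| Block | Contrasts | C24h in header | C24h in list |
|---|---|---|---|
| Part A formulation | 4 | yes | yes |
| Part A food effect | 2 | no | no |
| Part B dose | 3 | yes | yes |
| Part B food effect | 1 | no | no |
| Part B coating | 1 | yes | yes |

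C24h is missing for 2 + 1 = 3 contrasts and present for 4 + 3 + 1 = 8. Header and list agree in every block, so this is not a stray line lost from one list.

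**2. Strength of the conflict by part**

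- Part A: both food contrasts are at 240 mg. C24h is an endpoint of the primary high-fat objective (protocol 4, SAP 2.2), and protocol 10.4.1 requires it in the model. The conflict is direct.
- Part B: the single food contrast is at 480 mg, outside the wording of the 240 mg objective. Here the requirement rests on the model text of protocol 10.4.1, which states no dose limit, and on SAP Appendix 6.

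**3. Displays**

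Of the ten statistical-analysis tables (3.4–3.7 and 3.12–3.17), five titles name AUC and Cmax and five name Tmax. None names C24h. This does not separate food effect from the rest, because Tables 3.4, 3.12 and 3.16 also omit C24h although 8.1.5.1 lists it for those contrasts. The evidence is the endpoint lists, not the titles.

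**4. What remains without the ratio**

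C24h is summarised by prandial state in Tables 3.2, 3.3, 3.9 and 3.10, and individual parameters are in Listings 58 and 61. These do not give the model-based within-subject ratio and 90% CI.

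**5. Precision of the omitted estimate**

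Inputs: CVw for C24h = 44.9% (protocol 10.2); N = 12 and 16. Assumption: this CVw, given there for MR/IR and MR2/MR1, also applies to fed versus fasted.

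- sw = sqrt(ln(1 + 0.449²)) = 0.4285
- SE of the log ratio = sw × sqrt(2/N)
- CI limits for a ratio of 1.00 = exp(±t × SE), with t the 95th percentile

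The protocol's own figure first: Table 3 gives 36.2% for C24h at N = 12. The formula gives 36.9% with 11 df and 35.0% with 22 df, so the stated value is reproduced closely. At N = 16 Table 3 gives 29.9%; the formula gives 30.4% with 15 df and 29.3% with 30 df.

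The range below runs from a two-period analysis, df = N − 1, to the full six-period model, df = 5(N − 1).

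| CVw | N | df | Lower | Upper |
|---|---|---|---|---|
| 44.9% | 12 | 11 to 55 | 0.730 to 0.746 | 1.369 to 1.340 |
| 44.9% | 16 | 15 to 75 | 0.767 to 0.777 | 1.304 to 1.287 |
| 35% (illustrative) | 12 | 11 to 55 | – | 1.283 to 1.261 |
| 55% (illustrative) | 12 | 11 to 55 | – | 1.458 to 1.421 |

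These figures describe how precise the missing estimate would be. They do not measure harm from leaving it out.

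**The case against.** The best counter-argument is that the SAP has not dropped C24h at all. SAP 2.4 promises its CI, the general model in 8.1.5.1 is fitted to log C24h across all periods, and Appendix 6 includes C24h in Frel with fed versus fasted as a comparison. On that reading, only a contrast list is incomplete. This is accurate as description, but it shows the SAP contradicting itself, and the lists that pair endpoints with contrasts still exclude C24h. The formula printed in Appendix 6 also refers only to AUC or Cmax.

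Second, the protocol is itself mixed. FrelFE is based on AUC and Cmax only (protocol 4 and 10.4.1, SAP 2.2), the within-subject CV is requested only for AUC(0-inf) and Cmax, and the standard-breakfast and delayed-meal objectives omit C24h. These points stand and the descriptions need aligning. They do not cancel the separate instruction to model C24h for food effect.

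Third, SAP 2.1 compares itself with the protocol of 23 July 2018, which is not among the documents, so its statement cannot be shown to be false. This also stands. What is shown is a conflict with the current protocol. The amendment descriptions supplied do not mention adding C24h.

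Fourth, the impact is modest. No hypothesis is tested, descriptive C24h results by prandial state remain, and protocol 5.1.3 prefers the 18 to 24 hour samples over a single time point because of outliers. This limits the weight of the point, but the estimate is still specified in the protocol.

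**Conclusion.** The concern holds and should be fixed. Following the SAP's lists would leave out the fed/fasted C24h ratio and 90% CI for both Part A food contrasts, against a clear protocol requirement. It would also leave them out for the one Part B food contrast, where the requirement is arguable rather than explicit.

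The effect is on final reporting only (SAP 3.2); interim formulation selection is not affected. The conclusion about the omission rests on the text alone. Only the precision figures depend on an assumption, namely that the protocol's CVw carries over to fed versus fasted.

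**What to change.** - In SAP 8.1.5.1, add C24h (log scale) to the header and list of both food-effect blocks. Report the fed/fasted geometric mean ratio with 90% CI from the C24h model already specified.
- Name C24h in Tables 3.6 and 3.14 and, for consistency, in Tables 3.4, 3.12 and 3.16. Include it in Figures 3.7 and 3.14.
- Align the Frel formula and endpoint list in Appendix 6, and the FrelFE descriptions, with whatever is decided.
- If the omission is intended, declare and justify it in SAP 2.1, by reference to the current protocol, and amend Appendix 6.

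The cost is SAP wording, five table titles, two figures and one extra endpoint for three contrasts. No new data are needed.
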